#### Algorithm A: Phase III-IV Liver Chemistry Stopping and Increased Monitoring Algorithm

## Algorithm B: Phase III-IV Liver Chemistry Increased Monitoring Algorithm with Continued Therapy for ALT $\geq 3 \times$ ULN but $< 8 \times$ ULN

➤ See Appendix "Liver Safety: Required Actions and Follow-up Assessments and Study Treatment Rechallenge Guidelines".

➤ See Appendix "Liver Safety: Required Actions and Follow-up Assessments and Study Treatment Rechallenge Guidelines"

➤ All events of "possible Hy's Law" must be reported as an SAE. "Possible Hy's Law" is defined as a case in which ALT  $\geq 3 \times$  upper limit of normal (ULN) and total bilirubin  $\geq 2 \times$ ULN ( $> 35\%$  direct bilirubin), or ALT  $\geq 3 \times$ ULN and international normalized ration (INR)  $> 1.5$ ,\* if INR measured.

\* This INR threshold is not applicable to subjects receiving anticoagulant therapy.

Liver Safety Required Actions and Follow up Assessments Section can be found in [Appendix 6](#).

### 8.1.2. QTc Stopping Criteria

Details on performing ECG assessments can be found in Section [9.4.3..](#)

- The QTcF (QT interval corrected by Fridericia's formula) must be used for each individual participant to determine eligibility for and discontinuation from the study. This formula may not be changed or substituted once the participant has been enrolled.
- The QTcF must be continued to be used for all QTc data being collected from all subjects for data analysis. Safety ECGs and other non-protocol specified ECGs are an exception.
- The QTc should be based on single or averaged QTc values of triplicate electrocardiograms obtained over a brief (e.g., 5-10 minutes) recording period.
- For this study, the following QTc stopping criteria will apply:
  - QTcF  $> 500$  msec or uncorrected QT  $> 600$  msec
  - For patients with bundle branch block: QTcF  $\geq 530$  msec

- Change from baseline in QTcF > 60 msec

See the SoA for data to be collected at the time of treatment discontinuation and follow-up and for any further evaluations that need to be completed.

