6. Other diseases/abnormalities: Subjects with historical or current evidence of clinically significant cardiovascular, neurological, psychiatric, renal, hepatic, immunological, gastrointestinal, urogenital, nervous system, musculoskeletal, skin, sensory, endocrine (including uncontrolled diabetes or thyroid disease) or hematological abnormalities that are uncontrolled. Significant is defined as any disease that, in the opinion of the Investigator, would put the safety of the subject at risk through participation, or which would affect the efficacy or safety analysis if the disease/condition exacerbated during the study.
7. Unstable liver disease as defined by the presence of ascites, encephalopathy, coagulopathy, hypoalbuminemia, esophageal or gastric varices or persistent jaundice, cirrhosis, known biliary abnormalities (with the exception of Gilbert's syndrome or asymptomatic gallstones).

Note: Chronic stable hepatitis B and C are acceptable if the subject otherwise meets entry criteria.

8. Clinically significant ECG abnormality: Evidence of a clinically significant abnormality in the 12-lead ECG performed during screening. The Investigator will determine the clinical significance of each abnormal ECG finding in relation to the subject's medical history and exclude subjects who would be at undue risk by participating in the trial. An abnormal and clinically significant finding is defined as a 12-lead tracing that is interpreted as, but not limited to, any of the following:
  - Atrial fibrillation (AF) with rapid ventricular rate >120 beats per minute (BPM)

- Sustained or nonsustained ventricular tachycardia (VT)
- Second degree heart block Mobitz type II and third degree heart block (unless pacemaker or defibrillator had been inserted)
- QTcF  $\geq$ 500 msec in patients with QRS <120 msec and QTcF  $\geq$ 530 msec in patients with QRS  $\geq$ 120 msec

9. Unstable or life threatening cardiac disease: subjects with any of the following at screening (Visit 1) would be excluded:

- Myocardial infarction or unstable angina in the last 6 months
- Unstable or life threatening cardiac arrhythmia requiring intervention in the last 3 months
- New York Heart Association (NYHA) Class IV heart failure [[American Heart Association](#), 2016]

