## **8. DISCONTINUATION CRITERIA**

### **8.1. Discontinuation of Study Treatment**

A subject may be withdrawn from study treatment at any time. A reason for premature discontinuation of study treatment (e.g., AE, lack of efficacy [including acute moderate or severe asthma exacerbation], protocol deviation, Investigator discretion, consent withdrawn) must be captured in the CRF.

A subject must be withdrawn from study treatment if any of the following stopping criteria are met:

- Liver Chemistry: Meets any of the protocol-defined liver chemistry stopping criteria (see Section 8.1.1. and [Appendix 6](#)).
- QTc: Meets any of the protocol-defined stopping criteria (see Section 8.1.2.).
- Pregnancy: Positive pregnancy test (see Section 9.2.7. and [Appendix 4](#))

[figure not shown]

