### **8.1.3. Temporary Discontinuation**

A subject who discontinues the study treatment must be withdrawn from the study.

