## 9. STUDY ASSESSMENTS AND PROCEDURES

- Study procedures and their timing are summarized in the SoA (see [Table 1](#)).
- Protocol waivers or exemptions are not allowed.
- Immediate safety concerns should be discussed with the sponsor immediately upon occurrence or awareness to determine if the participant should continue or discontinue study treatment.
- Adherence to the study design requirements, including those specified in the SoA, is essential and required for study conduct.
- All screening evaluations must be completed and reviewed to confirm that potential participants meet all eligibility criteria. The investigator will maintain a screening log to record details of all participants screened and to confirm eligibility or record reasons for screening failure, as applicable.
- Procedures conducted as part of the participant's routine clinical management (eg, blood count) and obtained before signing of ICF may be utilized for screening or baseline purposes provided the procedure met the protocol-specified criteria and was performed within the time frame defined in the SoA.
- Repeat or unscheduled blood samples may be taken for safety reasons or for technical issues with the samples

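### The 530 msec QTcF limit depends on QRS width at entry but on bundle branch block for stopping, so a rare participant could be enrolled already over the mandatory stop (minor)

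*Protocol*

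**What the plan says.** **Entry.** Protocol 6.2, exclusion criterion 8, lists screening ECG findings that count as abnormal and clinically significant. Its last item sets the QTcF limit by QRS width: ≥500 "msec in patients with QRS <120 msec and QTcF" ≥530 msec where QRS is 120 msec or more. The list is not closed. It covers a tracing that "is interpreted as, but not limited to, any of the following", and the investigator is to "exclude subjects who would be at undue risk by participating in the trial".

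**Stopping.** Protocol 8.1.2 has an absolute stop at QTcF >500 msec (or uncorrected QT >600 msec) and one exception: "For patients with bundle branch block: QTcF" ≥530 msec. It adds a relative limb, "Change from baseline in QTcF > 60 msec". QRS width is not mentioned. The same section requires QTcF for both eligibility and discontinuation, so the two rules use the same measure.

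**Consequence.** Protocol 8.1 makes the stop mandatory: "A subject must be withdrawn from study treatment if any of the following stopping criteria are met". Section 8.1.3 adds: "A subject who discontinues the study treatment must be withdrawn from the study". Section 9 closes off exceptions: "Protocol waivers or exemptions are not allowed".

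**Timing.** The Schedule of Activities and SAP 8.6.2 place ECGs at Visit 1 (screening), Visit 3 (Week 4), Visit 5 (Week 24), Visit 7 (Week 52) and early withdrawal. None is scheduled at Visit 2, when dosing starts.

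**The concern.** An entry limit should be no looser than the stopping limit for the same measurement in the same person. Otherwise someone can be enrolled who already satisfies the reason to stop. Here the two limits match only if QRS of 120 msec or more and bundle branch block are the same condition, and neither document says they are. As a matter of clinical inference, a paced rhythm or a non-specific conduction delay can widen QRS without bundle branch block. Criterion 8 does not list high-grade heart block as excluding when a pacemaker or defibrillator is in place, so paced patients are not ruled out by that item.

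At stake is one participant's exposure and one misleading disposition entry. The participant would take the study drug for about four weeks and then have to leave the study. SAP 6.1.1 would count the case among the reasons for stopping treatment, although nothing had happened to the ECG on treatment.

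**Working it through.** The plan states no figure on this point, so there is none to reproduce. The check sets the two rules side by side for each combination of QRS width and bundle branch block. The inputs are the limits in exclusion criterion 8 and the absolute QTcF limits in 8.1.2.

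| QRS (msec) | Bundle branch block | Passes numeric entry limit if QTcF is | Absolute stop if QTcF is | Passes entry and meets stop |
|---|---|---|---|---|
| <120 | no | <500 | >500 | none |
| <120 | yes | <500 | ≥530 | none |
| ≥120 | yes | <530 | ≥530 | none |
| ≥120 | no | <530 | >500 | >500 to <530 |

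1. **Where the conflict lies.** It is confined to the last row. In whole milliseconds it covers 501 to 529, that is 529 − 501 + 1 = 29 values. A value of exactly 500 msec in the first row is excluded at entry but is not a stop. That is harmless, because entry is then the stricter rule.

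2. **Which limb is met.** On an unchanged ECG the change from baseline is 0 msec, so the >60 msec limb is not met. The absolute >500 msec limb is what ends treatment.

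3. **When it would show.** The first scheduled on-treatment ECG is at Week 4. A stop there forgoes 52 − 4 = 48 weeks of planned exposure, or 48/52 = 0.92 person-years.

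4. **Share of the study.** Protocol 10.1 plans 110 enrolled and 100 completing, which allows 110 − 100 = 10 drop-outs. One such case is 1/110 = 0.9% of participants and 1 of those 10.

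5. **How many to expect.** The documents give no prevalence for this group. Suppose a proportion p of enrolled participants falls in it after the investigator's judgement. The expected number is 110 × p:
   - p = 0.01%: 0.011
   - p = 0.1%: 0.11
   - p = 0.5%: 0.55

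   These values of p are assumptions, chosen only to show the order of size.

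6. **After the fix.** With the 530 msec entry limit restricted to bundle branch block with QRS ≥120 msec, and ≥500 msec excluding everyone else, the last row becomes entry <500 and stop >500. No value satisfies both. The other three rows do not change.

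**The case against.** The best reply is that the two rules do different jobs and both can be obeyed. Criterion 8 says which tracings bar entry; 8.1.2 says when dosing must end. A finding that is not on the list gives no right to stay on treatment, and a stop stricter than the entry limit errs on the cautious side. Criterion 8 is also open-ended, exclusion criterion 6 separately covers uncontrolled and clinically significant cardiovascular disease, and 8.1.2 itself refers to eligibility. For the failure to occur, an investigator must enrol someone whose screening QTcF already exceeds a printed mandatory stop.

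Most of this stands, and it is why the point is minor. It does not remove the mismatch. A limit written specifically for wide QRS tells the investigator that 501 to 529 msec is numerically acceptable, while 8.1.2 says that such a participant without bundle branch block must stop. Once the stop is met there is no discretion left to exercise.

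A reader might infer that the protocol exposes patients to a cardiac hazard. The documents do not support that. The investigator must already exclude those at undue risk, and where the rules disagree the outcome is that treatment ends. Nor does the mismatch reach every patient with wide QRS: those with bundle branch block have 530 msec at both points.

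**Conclusion.** The wording is wrong as it stands, and the point is minor. That the two conditions differ follows directly from the text and needs no assumption. The size does: probably 0 or 1 of 110 participants, resting on an assumed low prevalence and on investigators using the judgement that criterion 8 gives them.

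A reader might also infer that the safety results would be distorted. They would not. The study is descriptive, with no comparison between groups and no hypothesis test (Protocol 5.4, SAP 2.4). A participant withdrawn at Week 4 stays in the ITT population, and the data collected up to that point are summarised (SAP 4 and 11.7.1). The tables of QTcF change in SAP 8.6.2 would show that the ECG had not moved. No primary conclusion changes. The reason to act is that an entry rule and a mandatory stopping rule disagree and that a short wording change settles it.

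**What to change.** Leave 8.1.2 as it is, including the uncorrected QT >600 msec and >60 msec change limbs, so that no stopping limit is relaxed. Replace the last item of exclusion criterion 8 with: *QTcF ≥530 msec in patients who have bundle branch block and QRS ≥120 msec; QTcF ≥500 msec in all other patients.*

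**Cost.** This is a wording amendment, with the IRB/IEC approval that Protocol Appendix 2 requires for changes to the study design. It needs no new procedure: the site ECG machine already measures QRS (9.4.3), and bundle branch block must already be identified to apply 8.1.2. The SAP needs no change, because its ECG summaries do not use the entry limits.

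**Downside.** A rare patient with wide QRS, no bundle branch block and screening QTcF from 500 to just under 530 msec is not enrolled. The change also helps only patients who have not yet been enrolled.

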### **8.1.3. Temporary Discontinuation**

A subject who discontinues the study treatment must be withdrawn from the study.

### **8.1.4. Rechallenge**

#### **8.1.4.1. Study Treatment Restart or Rechallenge**

Study treatment restart or rechallenge after liver chemistry stopping criteria are met by any participant in this study is not allowed.

## **8.2. Withdrawal from the Study**

- A participant may withdraw from the study at any time at his/her own request, or may be withdrawn at any time at the discretion of the investigator for safety, behavioral, compliance or administrative reasons.
- If the participant withdraws consent for disclosure of future information, the sponsor may retain and continue to use any data collected before such a withdrawal of consent.
- If a participant withdraws from the study, he/she may request destruction of any samples taken and not tested, and the investigator must document this in the site study records.
- Refer to the SoA for data to be collected at the time of study discontinuation and follow-up and for any further evaluations that need to be completed.

### **8.3. Lost to Follow Up**

A participant will be considered lost to follow-up if he or she repeatedly fails to return for scheduled visits and is unable to be contacted by the study site.

The following actions must be taken if a participant fails to return to the clinic for a required study visit:

- The site must attempt to contact the participant and reschedule the missed visit as soon as possible and counsel the participant on the importance of maintaining the assigned visit schedule and ascertain whether or not the participant wishes to and/or should continue in the study.
- Before a participant is deemed lost to follow up, the investigator or designee must make every effort to regain contact with the participant (where possible, 3 telephone calls and, if necessary, a certified letter to the participant's last known mailing address or local equivalent methods). These contact attempts should be documented in the participant's medical record.

- Should the participant continue to be unreachable, he/she will be considered to have withdrawn from the study with a primary reason of lost to follow-up.

## 9. STUDY ASSESSMENTS AND PROCEDURES

- Study procedures and their timing are summarized in the SoA (see [Table 1](#)).
- Protocol waivers or exemptions are not allowed.
- Immediate safety concerns should be discussed with the sponsor immediately upon occurrence or awareness to determine if the participant should continue or discontinue study treatment.
- Adherence to the study design requirements, including those specified in the SoA, is essential and required for study conduct.
- All screening evaluations must be completed and reviewed to confirm that potential participants meet all eligibility criteria. The investigator will maintain a screening log to record details of all participants screened and to confirm eligibility or record reasons for screening failure, as applicable.
- Procedures conducted as part of the participant's routine clinical management (eg, blood count) and obtained before signing of ICF may be utilized for screening or baseline purposes provided the procedure met the protocol-specified criteria and was performed within the time frame defined in the SoA.
- Repeat or unscheduled blood samples may be taken for safety reasons or for technical issues with the samples

### Screening and critical baseline assessments

No study related procedures may be performed until the informed consent form has been signed by the subject. A pre-screening visit (Visit 0) is required in order to administer the informed consent before any changes are made to the subject's current medical regimen. Selection and modification of the subject's medications prior to study participation is based on the physician's judgment according to sound medical practice, principles, and each subject's needs. A subject's treatment must not be changed merely for the purpose of enabling the subject's participation in the study.

At the pre-screening visit (Visit 0) the following information will be assessed for each subject:

- Date of ICF signature
- Demographic information including race, age and gender
- Subject number
- Serious Adverse Event information (only in the case assessed as related to study participation)

The following additional critical baseline assessments will be conducted at screening (Visit 1):

- Weight and height
- Asthma diagnosis history including:
  - The age of the subject when they were first provided with an inhaler for asthma
  - Completion of an asthma medical history questionnaire (A copy of this questionnaire and instructions for its use can be found in the SRM.)
- Smoking history and status
- Exacerbation history
- Asthma and other concurrent medications and non-drug therapies
- Medical history including previous and/or concurrent medical conditions, detailed cardiovascular risk factor history, pneumonia, and pneumonia vaccine status
- Reason for screen failure (if applicable)
- Vital signs
- ACQ-6
- Inclusion/Exclusion criteria assessment
- Physical examination
- 12-lead ECG
- Child bearing status assessment for all potential female subjects
- Clinical laboratory tests (including hematology, clinical chemistry, urinalysis and serum pregnancy test)
- SAE assessment

In addition, the following procedures must be completed at screening (Visit 1):

- Review/dispense Medical Problems/Medication Taken worksheet
- Dispense salbutamol

## **9.1. Efficacy Assessments**

This is an open-label study and the efficacy will be assessed in an exploratory manner. Therefore, the efficacy endpoints are considered other endpoints and hence described in section 9.5. .

## 9.2. Adverse Events

The definitions of an AE or SAE can be found in [Appendix 3](#).

The investigator and any designees are responsible for detecting, documenting, and reporting events that meet the definition of an AE or SAE and remain responsible for following up AEs that are serious, considered related to the study treatment or the study, or that caused the participant to discontinue the study treatment/study (see Section 8.).

### 9.2.1. Time Period and Frequency for Collecting AE and SAE Information

- All SAEs will be collected from the start of study treatment until the follow-up visit at the time points specified in the SoA ([Table 1](#)). Any SAEs assessed as related to study participation (e.g., protocol-mandated procedures, invasive tests, or change in existing therapy) or related to a GSK product will be recorded from the time a subject consents to participate in the study up to and including any follow-up contact.
- All AEs will be collected from the start of treatment until the follow-up visit at the time points specified in the SoA ([Table 1](#)).
- Medical occurrences that begin before the start of study treatment but after obtaining informed consent will be recorded on the Medical History/Current Medical Conditions section of the case report form (CRF) not the AE section.
- All SAEs will be recorded and reported to the sponsor or designee within 24 hours, as indicated in [Appendix 3](#). The investigator will submit any updated SAE data to the sponsor within 24 hours of it being available.
- Investigators are not obligated to actively seek AEs or SAEs in former study participants. However, if the investigator learns of any SAE, including a death, at any time after a participant has been discharged from the study, and he/she considers the event to be reasonably related to the study treatment or study participation, the investigator must promptly notify the sponsor.
- The method of recording, evaluating, and assessing causality of AEs and SAEs and the procedures for completing and transmitting SAE reports are provided in [Appendix 3](#).

### 9.2.2. Method of Detecting AEs and SAEs

Care will be taken not to introduce bias when detecting AE and/or SAE. Open-ended and non-leading verbal questioning of the participant is the preferred method to inquire about AE occurrence.

### 9.2.3. Follow-up of AEs and SAEs

After the initial AE/SAE report, the investigator is required to proactively follow each participant at subsequent visits/contacts. All AE/SAEs will be followed until the event is resolved, stabilized, otherwise explained, or the participant is lost to follow-up (as defined in Section 8.3.). Further information on follow-up procedures is given in [Appendix 3](#).

### 9.2.4. Regulatory Reporting Requirements for SAEs

- Prompt notification by the investigator to the sponsor of a SAE is essential so that legal obligations and ethical responsibilities towards the safety of participants and the safety of a study treatment under clinical investigation are met.
- The sponsor has a legal responsibility to notify both the local regulatory authority and other regulatory agencies about the safety of a study treatment under clinical investigation. The sponsor will comply with country-specific regulatory requirements relating to safety reporting to the regulatory authority, Institutional Review Boards (IRB)/Independent Ethics Committees (IEC), and investigators.
- Investigator safety reports must be prepared for suspected unexpected serious adverse reactions (SUSAR) according to local regulatory requirements and sponsor policy and forwarded to investigators as necessary.
- An investigator who receives an investigator safety report describing a SAE or other specific safety information (eg, summary or listing of SAE) from the sponsor will review and then file it along with the Investigator's Brochure and will notify the IRB/IEC, if appropriate according to local requirements.

